## 16.4 Security and Archival of Data

The Rave EDC and Rave eCOA/ePRO systems are hosted by Medidata; the data are stored at Medidata's primary data center in Houston, Texas, with fail-safe data centers in New Jersey. Data are regularly backed up by Medidata.

Medidata maintains 21 CFR Part 11-compliant electronic systems, with procedures in place to safeguard against unauthorized acquisition of data. Any authorized communication with the Medidata servers at the Houston Data Center is conducted via SSL (128-bit) encryption. Robust password procedures, consistent with 21 Part 11, are in place. Robust physical security procedures are in place at the Houston Data Center to prevent unauthorized personnel physical access to the server rooms. EDC account access is maintained and monitored by the Biostatistics and Clinical Data Management group of the TDNCC.

Other databases will be stored on Seattle Children's servers and are safeguarded against unauthorized access by established security procedures. Network accounts are password protected and maintained and monitored by Seattle Children's. Data is backed up regularly according to the Information Services group's procedures.

### **16.5 Availability and Retention of Investigational Records**

The Investigator must make study data accessible to the monitor, other authorized representatives of the Sponsor (or designee), IRB, and Regulatory Agency (e.g., FDA) inspectors upon request. A file for each subject must be maintained that includes the signed Informed Consent, HIPAA Authorization and Assent Form and copies of all source documentation related to that subject. The Investigator must ensure the reliability and availability of source documents from which the information on the CRF was derived.

All study documents (e.g., patient files, signed informed consent forms, copies of CRFs, Essential Document and Study Reference Binders) must be kept secured for a period of five years after database lock. There may be other circumstances for which the Sponsor is required to maintain study records and, therefore, the Sponsor should be contacted prior to removing study records for any reason.

### **16.6 Monitoring**

By signing this protocol, the Investigator grants permission to the Sponsor (or designee), and appropriate regulatory authorities to conduct on-site monitoring and/or auditing of all appropriate study documentation. Monitoring visits will be conducted by representatives of the Sponsor according to the U.S. CFR 21 Part 312 to ensure investigator compliance to 21 CFR Parts 50, 56 and 312.

### **16.7 Subject Confidentiality**

In order to maintain subject confidentiality, only a site number and subject number will identify all study subjects on CRFs and other documentation submitted to the Sponsor. The subject's CFF patient registry number will also be collected. Additional subject confidentiality issues (if applicable) are covered in the Clinical Study Agreement.

## **17 ADMINISTRATIVE, ETHICAL, REGULATORY CONSIDERATIONS**

The study will be conducted according to the Declaration of Helsinki, Protection of Human Volunteers (21 CFR 50), Institutional Review Boards (21 CFR 56), and Obligations of Clinical Investigators (21 CFR 312).

Clinical information will not be released without written permission of the subject, except as necessary for monitoring by the FDA. The Investigator must also comply with all applicable privacy regulations (e.g., Health Insurance Portability and Accountability Act of 1996, EU Data Protection Directive 95/46/EC).

### **17.1 Protocol Amendments**

Any amendment to the protocol will be written by the Sponsor. Protocol amendments cannot be implemented without prior written IRB approval except as necessary to eliminate immediate safety hazards to patients. A protocol amendment intended to eliminate an apparent immediate

hazard to patients may be implemented immediately, provided the IRBs are notified within five working days.

## 17.2 Institutional Review Boards and Independent Ethics Committees

The protocol and consent form will be reviewed and approved by the IRB on record prior to study initiation. The Investigator will keep the IRB informed as to the progress of the study. The Investigator will obtain assurance of IRB compliance with regulations.

Any documents that the IRB may need to fulfill its responsibilities (such as protocol, protocol amendments, consent forms, information concerning patient recruitment, payment or compensation procedures, or other pertinent information) will be submitted to the IRB. The IRB's written unconditional approval of the study protocol and the informed consent form will be in the possession of the Investigator before the study is initiated. The IRB's unconditional approval statement will be transmitted by the Investigator to the Sponsor or designee prior to the shipment of study supplies to the site. This approval must refer to the study by exact protocol title and number and should identify the documents reviewed and the date of review.

Protocol and/or informed consent modifications or changes may not be initiated without prior written IRB approval except when necessary to eliminate immediate hazards to the patients or when the change(s) involves only logistical or administrative aspects of the study. Such modifications will be submitted to the IRB and written verification that the modification was submitted and subsequently approved should be obtained.

The IRB must be informed of revisions to other documents originally submitted for review; serious and/or unexpected adverse experiences occurring during the study in accordance with the standard operating procedures and policies of the IRB; new information that may affect adversely the safety of the patients of the conduct of the study; an annual update and/or request for re-approval; and when the study has been completed.

## 17.3 Informed Consent Form

Informed consent will be obtained in accordance with the Declaration of Helsinki, US Code of Federal Regulations for Protection of Human Subjects (21 CFR 50.25[a,b], CFR 50.27, and CFR Part 56, Subpart A), the Health Insurance Portability and Accountability Act (HIPAA, if applicable), and local regulations.

The Investigator will prepare the informed consent form, assent and HIPAA authorization and provide the documents to the Sponsor or designee for approval prior to submission to the IRB. The consent form generated by the Investigator must be acceptable to the Sponsor and be approved by the IRB. The written consent document will embody the elements of informed consent as described in the International Conference on Harmonisation and will also comply with local regulations. The Investigator will send an IRB-approved copy of the Informed Consent Form to the Sponsor (or designee) for the study file.

A properly executed, written, informed consent will be obtained from each subject prior to entering the subject into the trial. Information should be given in both oral and written form and subjects (or their legal representatives) must be given ample opportunity to inquire about details of the study. If appropriate and required by the IRB, assent from the subject will also be obtained. If a subject is unable to sign the informed consent form (ICF) and the HIPAA authorization, a legal representative may sign for the subject. A copy of the signed consent form

(and assent) will be given to the subject or legal representative of the subject and the original will be maintained with the subject's records.

During the course of the study, if modifications are made to the consent form that impact the subject, the subject will be re-consented as described above.

#### **17.4 Consent for Collection and Use of CFF Registry ID Number**

To facilitate the inclusion of retrospective and prospective information from all patients enrolled in this study, the subject's CFF Registry ID number will be collected. The Cystic Fibrosis Foundation Patient Registry (CFFPR) collects data on all CF patients who consented to participate in the CFFPR registry and who are followed at CFF-accredited care centers. The registry data includes information from clinical encounters, hospitalizations courses of antibiotics, and year-end surveys. Data also include microbiology results, spirometry results, CF genotype and other information. The patient's CF registry number will be recorded in the CRF.

#### **17.5 Publications**

The preparation and submittal for publication of manuscripts containing the study results shall be in accordance with a process determined by mutual written agreement among the study Sponsor and participating institutions. The publication or presentation of any study results shall comply with all applicable privacy laws, including, but not limited to, the Health Insurance Portability and Accountability Act of 1996.

#### **17.6 Investigator Responsibilities**

By signing the Agreement of Investigator form, the Investigator agrees to:

- 1 Conduct the study in accordance with the protocol and only make changes after notifying the Sponsor (or designee), except when to protect the safety, rights or welfare of subjects.
- 2 Personally conduct or supervise the study (or investigation).
- 3 Ensure that the requirements relating to obtaining informed consent and IRB review and approval meet federal guidelines, as stated in § 21 CFR, parts 50 and 56.
- 4 Report to the Sponsor or designee any AEs that occur in the course of the study, in accordance with §21 CFR 312.64.
- 5 Ensure that all associates, colleagues and employees assisting in the conduct of the study are informed about their obligations in meeting the above commitments.
- 6 Maintain adequate and accurate records in accordance with §21 CFR 312.62 and to make those records available for inspection with the Sponsor (or designee).
- 7 Ensure that an IRB that complies with the requirements of §21 CFR part 56 will be responsible for initial and continuing review and approval of the clinical study.
- 8 Promptly report to the IRB and the Sponsor (or designee) all changes in the research activity and all unanticipated problems involving risks to subjects or others (to include amendments and IND safety reports).
- 9 Seek IRB approval before any changes are made in the research study, except when necessary to eliminate hazards to the patients/subjects.

10 Comply with all other requirements regarding the obligations of clinical investigators and all other pertinent requirements listed in § 21 CFR part 312.

**APPENDIX. SCHEDULE OF EVENTS**

	ENROLLMENT VISIT (DAY 1)	DAY 7 A (+ 1 day)	DAY 14 A (+ 1 day)	DAY 28 A (+ 1 day)
Informed Consent	X			
Review Eligibility	X			
CFF Registry ID, CF Diagnosis, and Demographics	X			
Medical History/GI History	X			
Concomitant Medication Review	X			
Height	X			
Weight	X			
Assist with downloading mobile application for completing questionnaires	X			
Complete PAC-SYM and PAGI-SYM questionnaires and disease-specific questions on mobile device	X	X	X	X
Complete PAC-QOL on mobile device	X			X

A The Questionnaire(s) will be completed outside-the-clinic.

GALAXY Statistical Analysis Plan

PROTOCOL NUMBER: GALAXY-OB-18

PROTOCOL TITLE: Multicenter Study of Patient-Reported Gastrointestinal Symptoms in People with Cystic Fibrosis (GALAXY)

PRINCIPAL INVESTIGATOR: A. [name], MSc
[name], MSc
[name]

FUNDING AGENCIES: Cystic Fibrosis Foundation
[name]
Bethesda, MD
20814

PREPARED BY: [name]
[name], MS
[name]

RELEASE DATE: 12/16/2019

Signature Page

[figure not shown]
GALAXY Statistical Analysis Plan (12/16/2019) approved by:

A. [name], MSc
Principal Investigator

12/18/19
Date

[name], MSc
Principal Investigator

12/19/19
Date

[name]
Principal Investigator

12/20/19
Date

PREFACE

The Statistical Analysis Plan (SAP) as outlined in this document will be finalized prior to the analysis of final study data. The SAP contains all modifications and updates to the planned analyses that were outlined in the original study protocol. The analyses that will be generated for the final statistical report are outlined in this document. This plan details all a priori specified analyses that will be performed upon study completion and database lock, with detailed specifications for all tables, figures, and statistical models.

1. Overview

This is a prospective, multicenter, observational study designed to collect gastrointestinal (GI) related data in patients with cystic fibrosis (CF).

Eligible participants were consented and enrolled in the study at the Enrollment or Baseline Visit. At the visit, the participant or parent/guardian completed the patient reported outcome surveys (PROs) using their mobile device (e.g., smartphone or tablet). The PROs consist of four questionnaires: Patient Assessment of Constipation-Symptoms (PAC-SYM), Patient Assessment of Gastrointestinal-Symptoms (PAGI-SYM), Patient Assessment of Constipation Quality of Life (PAC-QOL) and the disease-specific questionnaire. The disease-specific questionnaire included the Bristol Stool Scale and collected information on presence of fecal incontinence, stool quality and stool frequency.

At the Baseline Visit, weight and height were collected in addition to medical history and concomitant medication information. The participant or parent/guardian completed the PROs outside-the-clinic setting per the Schedule of Events using their mobile device. Participants were on study for up to 29 days.

2. Report Generation

2.1 Data Flow

An electronic data capture system, Medidata Rave, was utilized for collection of study data. Study personnel at each site entered data from a participant's visit onto the protocol-specific Case Report Form (eCRF). Study participants were not be identified by name in the study database or on any data capture screens, however, they were identifiable by a unique participant identification number. Only study personnel at the individual sites were able to link the study ID to the participant's name. The Medidata Rave eCOA/ePRO system, a regulatory compliant system which allows participants in a study using Medidata Rave EDC to complete and submit forms and data for patient-reported outcomes electronically on a mobile device to the Medidata Rave EDC System, was also utilized. Study personnel at each site registered study participants using their unique identification number which generated an activation code unique to that participant. Study site personnel provided the participant with their activation code. The study participant downloaded the Medidata Rave eCOA/ePRO app to their mobile device and used their unique activation code to create their ePRO login and password.

The following schedule of events shows the schedule and data collected at the baseline visit and outside-of-clinic follow-up.

	BASELINE VISIT (DAY 1)	DAY 7 (+ 1 day)	DAY 14 (+ 1 day)	DAY 28 (+ 1 day)
Informed Consent	X			
Review Eligibility	X			
CFF Registry ID, CF Diagnosis, and Demographics	X			
Medical History/GI History	X			
Concomitant Medication Review	X			
Height	X			
Weight	X			
Assist with downloading mobile application for completing questionnaires	X			
Complete PAC-SYM, PAGI-SYM, and disease-specific questionnaires on mobile device	X	X	X	X
Complete PAC-QOL	X			X

After data was entered into the study database, data validation checks were applied on a regular basis. Queries were entered, tracked, and resolved through the system directly. The study database was updated in accordance with the resolved queries. All changes to the study database were documented in an audit trail.

2.2 Report Generation

The final statistical report will describe and provide justification for any deviations from the original statistical analysis plan as described in the protocol. Analyses will be performed using the most current versions of SAS software or R. All programs used to produce this report will be documented, tested, and archived. All tables, figures, and listings will be validated before considered final.

2.3 Definition of the Analysis Populations

Enrollment:

An enrolled participant was defined as a participant who had met all eligibility criteria, and fully completed (i.e. no question left unanswered) at least one of the ePRO questionnaires (PAC-SYM, PAGI-SYM, PAC-QOL, and disease-specific) at baseline.

Baseline:

Baseline refers to the enrollment visit of enrolled participants, at which informed consent was given, eligibility was met, and medical history was collected.

Follow-up weeks:

GALAXY Statistical Analysis Plan 12/16/2019 - CONFIDENTIAL

Follow-up occurred at week 1 (day 7, +1), week 2 (day 14, +1), and week 4, (day 28, +1). These were outside-of-clinic, i.e. participants are asked to complete the ePRO via their mobile devices. The questionnaires took approximately 10 minutes to complete. For participants \geq 2 years of age to $<$ 12 years of age, the parent/guardian completed the questionnaire. For participants \geq 12 years of age, the participant completed the questionnaire.

Protocol-defined constipation:

Per protocol, constipation is defined as $<$ 3 bowel movements in the past week and/or Bristol Stool type 1 or 2.

3. Overview of Planned Analyses

Unless otherwise noted, the endpoints of this study are mostly descriptive, with all continuous outcomes such as symptom severity and PRO scores evaluated using descriptive statistics such as mean, median, standard deviation, and 95% confidence intervals. Presence/absence of symptoms will be shown as percentages and corresponding 95% confidence intervals calculated using the Wilson method. Longitudinal models will be mixed-effect models with participant-specific random effect and compound symmetry covariance structure. Except where otherwise noted, all tests will be two-sided and statistical significance will be determined at the 0.05 level. No adjustment for multiple comparisons will be made.

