## 4 STUDY DESIGN

### 4.1 Study Overview

This is a prospective, multicenter, observational study designed to collect gastrointestinal related data in patients with CF.

Eligible subjects will be consented and enrolled in the study at the Enrollment Visit. At the visit, the subject or parent/guardian will complete the PROs using their mobile device (e.g., smartphone or tablet). The PROs will consist of four questionnaires: Patient Assessment of Constipation-Symptoms (PAC-SYM), Patient Assessment of Gastrointestinal-Symptoms (PAGI-SYM), Patient Assessment of Constipation Quality of Life (PAC-QOL) and the disease-specific questionnaire. The disease-specific questionnaire will include the Bristol Stool Scale and will collect information on presence of fecal incontinence, stool quality and frequency. At the Enrollment Visit, weight and height will be collected in addition to medical history and concomitant medication information. The subject or parent/guardian will complete the PROs outside-the-clinic setting per the Schedule of Events using their mobile device.

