### 6.5 Screen Fail Criteria

Any consented patient who is excluded from the study before enrollment is considered a screen failure. All screen failures must be documented with the reason for the screen failure adequately stated. If a subject screen fails prior to enrollment, they can be rescreened if the site staff feels they meet eligibility criteria. Rescreened subjects will have to complete all screening procedures (i.e., data from previous screenings cannot be used).

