## **12 DISCONTINUATION AND REPLACEMENT OF SUBJECTS**

### **12.1 Early Withdrawal of Subjects from the Study**

All subjects are free to withdraw from participation at any time, for any reason, specified or unspecified, and without prejudice. This may include subjects who withdraw from completing the study visit and who decline to complete the questionnaires.

If the investigator is able to provide a reason for early subject withdrawals, it will be specified in the subject's source documents.

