#### 15.1.1 Data Sets Analyzed

The analysis population consists of all eligible subjects who enroll into the study – the Full Analysis Set. For select endpoints, stratification of study results by age group, CF genotype, pancreatic status, and whether sites were DIGEST awardees will also be considered.

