### 15.3 Analysis of Primary Endpoint

The primary endpoint is the percentage of scheduled outside-the-clinic assessments with at least one PRO fully completed out of the four questionnaires administered (the PAC-SYM, PAGI-SYM, PAC-QOL and the disease-specific questionnaire). The denominator for the percentage is the expected number of outside-the-clinic assessments (# of enrolled subjects x 3 outside-the-clinic assessments/subject).

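### SAP 2.3 adds a fully completed baseline ePRO to the meaning of enrolled, so the primary feasibility percentage applies to baseline completers; SAP 3.3 and Exhibit 3.1 should say so and show the all-eligible figure beside it

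*SAP*

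**What the plan says.** Protocol 4.1 states: "Eligible subjects will be consented and enrolled in the study at the Enrollment Visit". Protocol 15.1.1 states: "The analysis population consists of all eligible subjects who enroll into the study", and calls this the Full Analysis Set. Protocol 15.3 sets the primary denominator as the number "of enrolled subjects x 3 outside-the-clinic assessments/subject".

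The protocol separates consent from enrollment. Section 6.5 says: "Any consented patient who is excluded from the study before enrollment is considered a screen failure". Inclusion criteria 5 and 6 ask for willingness to answer on a mobile device and ability to use the app. Section 10.1 lists the baseline questionnaires as step 9 of the Enrollment Visit, after the eligibility review (step 3) and app set-up (step 8). None of these sections makes a completed questionnaire a condition of enrollment.

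SAP 2.3 defines an enrolled participant as one who "met all eligibility criteria, and fully completed (i.e. no question left unanswered) at least one of the ePRO questionnaires" at baseline. The same condition appears in footnote 3 of Exhibit 1.1, footnote 1 of Exhibit 2.1 and the text of Exhibit 3.2.1. SAP 3.3 restates the primary endpoint, adds an analysis by age group, and gives no denominator of its own. Neither SAP 3.3 nor the completion table (Exhibit 3.1) repeats the condition.

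**The concern.** The primary objective is whether electronic questionnaires can be completed outside the clinic, and an assessment counts as a success when at least one PRO is fully completed. SAP 2.3 applies the same criterion at baseline to decide who enters the denominator. An eligible person who left an item blank in every form begun at baseline, or who stopped before finishing one, contributes no assessments to the primary endpoint. Baseline takes place in clinic, with staff helping to set up the app, so someone who finishes no form there could plausibly do worse at home.

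Completion among people who have completed once is a legitimate quantity. It is narrower than completion among everyone who consented and was eligible, and a reader who takes the headline percentage from SAP 3.3 or Exhibit 3.1 would not be told which of the two it is. What is at stake is how the headline figure of a feasibility study is defined and labelled.

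**Working it through.** **The plan's own figure.** The plan sets no target, threshold or precision for the primary percentage. Its one sample-size figure, about 400, comes from constipation prevalence (Protocol 15.7). It reproduces: 1.96² × 0.25 × 0.75 / 0.045² = 355.7, so 356. Allowing for 12% missing gives 356 / 0.88 = 405, or 356 × 1.12 = 399. The present point does not enter that calculation.

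**Formula.** Let f be the share of eligible people excluded by the baseline condition, c the follow-up completion rate among SAP-enrolled participants, and cx the rate among those excluded.

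- All-eligible rate = (1 − f)c + f·cx.
- SAP rate minus all-eligible rate = f(c − cx).

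The shift is zero if f = 0 or cx = c, and upward only if f > 0 and cx < c. The documents give none of the three values, so every input below is an assumption.

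**Numbers.** Take 400 SAP-enrolled participants and c = 85%: 400 × 3 = 1,200 assessments, of which 0.85 × 1,200 = 1,020 are completed. With x people excluded, f = x / (400 + x). At cx = 0 the all-eligible rate is 1,020 / [3(400 + x)].

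| Excluded x | f | Rate, cx = 0 | Shift, cx = 0 | Rate, cx = c/2 | Shift, cx = c/2 |
|---|---|---|---|---|---|
| 2 | 0.5% | 84.58% | 0.4 points | 84.79% | 0.2 points |
| 4 | 1.0% | 84.16% | 0.8 points | 84.58% | 0.4 points |
| 8 | 2.0% | 83.33% | 1.7 points | 84.17% | 0.8 points |
| 21 | 5.0% | 80.76% | 4.2 points | 82.88% | 2.1 points |

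At cx = 0 this is 0.85 points per 1% excluded.

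**Scale.** The Wilson 95% interval at 85% is 82.87% to 86.91% (half-width 2.02 points) if the 1,200 assessments are treated as independent. It is 81.17% to 88.17% (half-width 3.50 points) if responses are fully clustered within person (n = 400). The share at which the shift equals the half-width is f = half-width / (c − cx), or 400f / (1 − f) people:

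- Independent, cx = 0: 2.02 / 85 = 2.4%, about 10 people.
- Independent, cx = c/2: 2.02 / 42.5 = 4.8%, about 20 people.
- Clustered, cx = 0: 3.50 / 85 = 4.1%, about 17 people.
- Clustered, cx = c/2: 3.50 / 42.5 = 8.2%, about 36 people.

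For independent assessments and cx = 0, the tipping share is 3.7% at c = 70% (half-width 2.59) and 1.3% at c = 95% (half-width 1.24).

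**The case against.** The strongest reply is that SAP 2.3 fills a gap. The protocol does not define enrolled, it separates consent from enrollment, and it places the questionnaires within the Enrollment Visit. One completed form of four can be read as putting inclusion criteria 5 and 6 into practice. This stands: a reader might infer that the SAP contradicts the protocol, but there is no explicit definition for it to contradict.

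A reader might also look to Protocol 12.1, which says of early withdrawal: "This may include subjects who withdraw from completing the study visit and who decline to complete the questionnaires". It is tempting to conclude that people who decline at baseline are enrolled subjects who withdrew. The text does not support that. It is permissive, it does not say whether the declining happens at baseline or later, and the protocol also uses the word subject for people not yet enrolled (sections 6.5 and 16.1). I place no weight on it.

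Nor is the condition hidden, as it is written in four places in the SAP. The SAP may modify the plan; its preface says: "The SAP contains all modifications and updates to the planned analyses that were outlined in the original study protocol". Nothing there requires each change to be flagged singly, and SAP 2.2 commits the final report to "describe and provide justification for any deviations from the original statistical analysis plan as described in the protocol".

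Exhibit 1.1 will show Eligible, Enrolled and weekly completion totals, so a reader could form (Week 1 + Week 2 + Week 4) / (3 × Eligible). That is true, but the percentage is not itself a planned result, and the exhibit does not say whether excluded people were sent follow-up questionnaires, without which the derived figure cannot be interpreted.

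Finally, the endpoint concerns scheduled assessments outside the clinic. If excluded people were never scheduled for any, counting three failures for each mixes set-up failure in clinic with feasibility at home. That is fair. It is a reason to show the all-eligible figure beside the SAP figure, suitably labelled, and not in its place.

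**Conclusion.** The concern holds in a limited form. SAP 2.3 adds a condition that the protocol does not state, and because the denominator is built on enrolled participants, the primary percentage is conditional on having completed a form at baseline. The SAP discloses the condition, but not where the primary endpoint and its completion table are set out.

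A reader might infer that the planned percentage is inflated. The documents do not show this: they do not indicate that anyone was excluded, and they give no completion rates. Exclusion requires failing to finish any of four forms, in clinic, after selection for willingness and ability, so the shift may be near zero. It would exceed the narrower 2.02-point half-width only above about 10 exclusions among 400 SAP-enrolled, and then only under the extreme assumption that those excluded complete nothing (c = 85%). No test or threshold depends on the figure, and the sample size is unaffected. The importance is minor to moderate, and the case for acting rests mainly on how cheap the change is.

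**What to change.** - In SAP 2.3, SAP 3.3 and Exhibit 3.1, state that the primary percentage is among participants who fully completed at least one ePRO at baseline, and that this condition was added to the protocol's wording.
- Add one row giving the percentage over 3 × all consented, eligible participants (the Eligible column of Exhibit 1.1), with assessments lacking a fully completed PRO counted as not completed. Give the number excluded by the baseline condition next to it.
- State whether excluded people were scheduled for and sent the follow-up questionnaires and reminders. If they were not, label the added row a lower bound.

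The cost is one sentence, repeated where the endpoint is reported, and one row from counts already planned. The second figure may be slightly less favourable, and it may be interpretable only as a lower bound. If nobody was excluded, the two percentages coincide and the question is closed.
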